## Research Protocol

1 \* Do you have a research protocol to upload?

- Yes
- No, I do not have a research protocol and will use the CICERO application to enter my study information

2 If Yes, upload the research protocol:

Name	Created	Modified Date
------	---------	---------------

There are no items to display

ID: VIEW4E00563F8D000  
Name: v2\_Research Protocol

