## Justification, Objective, & Research Design

**If you uploaded a separate research protocol document in the 'Research Protocol' page, cite the applicable section and page numbers from that document in the answer boxes below.**

1 \* Describe the purpose, specific aims, or objectives of this research. State the hypothesis to be tested:

To determine if a new assay to detect early biofilm colonization can be validated in acute postoperative wound infections in orthopaedic trauma patients who have sustained high energy open/closed lower extremity fractures. This would potentially help decrease the amount of surgical interventions needed for infections as it could allow for early intervention and antibiotics.

2 \* Discuss the research design including but not limited to such issues as: probability of group assignment, potential for subject to be randomized to placebo group, use of control subjects, etc.:

A prospective trial conducted at Shock Trauma of patients between 18 years of age and older who have sustained a fracture with metal implanted. We will be collecting between 1-3 routine blood draws for the purpose of laboratory analysis to assess biofilm growth. Patients may be infected or non-infected at the time of blood draw; they will be selected at random for purposes of this study. All patients will be followed as standard of care by their treating physician for all their follow up visits.

3 \* Describe the relevant prior experience and gaps in current knowledge. Describe any relevant preliminary data:

Surgical site infection in the orthopaedic surgery population is a significant public health issue. Wound infections result in both increased length of hospital stay and total cost of care. Specifically, a biofilm assay would help identify early infection in patients and potentially reduce the need for re-operations for infections as it would allow early antibiotic delivery to the affected areas. Our bacteria of focus would be Methicillin-resistant Staphylococcus aureus (MRSA), as this is one of the most predominant organisms in orthopaedic surgical site infections, but can be included to other pathogens causing surgical site infections.

4 \* Provide the scientific or scholarly background, rationale, and significance of the research and how it will add to existing knowledge:

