## Study Procedures

**If you uploaded a separate research protocol document in the 'Research Protocol' page, cite the applicable section and page numbers from that document in the answer boxes below. (If this study is a collaborative UM/VA study please list each procedure that is being conducted and the locations where it is being conducted.)**

1 \* Describe all procedures being performed for research purposes only (these procedures would not be done if individuals were not in the study) and when they are performed, including procedures being performed to monitor subjects for safety or to minimize risks:

Patients will be identified at random in the orthopaedic trauma clinic and current admitted patients who have been diagnosed with an infection. Once eligibility has been confirmed, the informed consent process will be completed by the Research Coordinator and the attending surgeon. Patients will be approached about potential participation in the study as soon as is feasible following determination of eligibility.

Once consented into the study, baseline data regarding participant characteristics, injury characteristics, fracture classification and medical history/co-morbidities will be collected. Characteristics about hospital course and treatment received will also be collected (i.e. blood culture results, antibiotic usage, etc).

At each follow up visit, participants will undergo a clinical evaluation by the treating surgeon as part of standard of care following any surgical procedure and will be interviewed by the research coordinator. Blood draws will be taken at the initial and each subsequent visit and will be analyzed in the laboratory of one of the investigators in the study. If the patient is currently infected currently, or become infected at any point in the future, additional blood draws may be taken, at a maximum of 10 draws, over the period of two years from the clinical diagnosis of infection. The amount of blood that is drawn will not exceed 50 ml or 3 ml per kg in a 8 week period, and collection may not occur more frequently than 2 times per week.

Finally, we would prospectively correlate the laboratory findings with clinical findings by searching the patients' medical records to find outcomes such as a biofilm formation.

2 \* Describe all procedures already being performed for diagnostic or treatment purposes (if not applicable to the study, enter "N/A"):

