## Sample Size and Data Analysis

**If you uploaded a separate research protocol document in the 'Research Protocol' page, cite the applicable section and page numbers from that document in the answer boxes below.**

1 \* Provide the rationale and sample size calculations for the proposed target population:

In order to validate the designed test, we hypothesize needing a large study to determine if it is effective in a human model. Additionally, we will follow out the patients to determine if some become infected (the primary outcome of the study that we are trying to ultimately be able to predict. We anticipate 1000-1200 patients enrolled in this study).

2 \* Provide the plan for data analysis. Include in the description the types of comparisons that are planned (e.g., comparison of means, comparison of proportions, regressions, analysis of variance, etc.), which is the primary comparison/analysis, and how the analyses proposed will relate to the primary purposes of the study:

We will describe the population in terms of general descriptive statistics for age, injury, surgery and outcome. We will use t-testing and other statistical analysis as appropriate.

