## Protected Health Information (PHI)

You indicated that HIPAA applies and the study will view, access, share, collect, use, or analyze health information that is individually identifiable.

1 \* Which PHI elements will be used or disclosed in this study? (Check all that apply)

Name  
 Address (if more specific than Zip Code)  
 Dates  
 Ages over age 89  
 Telephone numbers  
 Fax numbers  
 Email addresses  
 Social Security numbers  
 Medical record numbers  
 Health plan beneficiary numbers  
 Account numbers

- Certificate/license numbers
- Vehicle identifiers and serial numbers, including license plate numbers
- Device identifiers and serial numbers
- Web universal resource locators (URLs)
- Internet protocol (IP) address numbers
- Biometric identifiers, including fingerprints and voiceprints
- Full-face photographic images and any comparable images
- Any other unique identifying number, characteristic, or code, unless otherwise permitted by the Privacy Rule for re-identification
- None

2 \* Why is the PHI necessary for this research?

*If SSNs are going to be used, describe the specific use and type of SSN to be used (real, scrambled, last 4 digits).*  
Used to correspond name and MRN to specific code to file. Patient records will be accessed to determine clinical correlation to biofilm assay.

3 \* What is the source(s) of the PHI?

Medical record.

4 \* Provide written assurance that Protected Health Information will not be reused. (Note: this refers to re-use on another study or for a purpose which has not been approved, not to the re-use of screening data during the current study).  
PHI will not be used but for purposes of our study.

5 \* How will permission to allow the use/disclosure of the individual's protected health information (PHI) be obtained? (Choose all that apply:)

- Obtain written authorization (*upload authorization form at the end of the application under "Consent and HIPAA Authorization Forms"*)
- Requesting waiver/alteration of authorization (includes waiver of authorization for recruitment only)
- Qualifies as a limited data set (LDS)

5.1 If you are using a limited data set (LDS), please attach the Data Use Agreement (DUA):

Name	Created	Modified Date
------	---------	---------------

There are no items to display

ID: VIEW4E1B0A24AA400  
Name: v2\_Protected Health Information

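### The study aims to validate an assay, but the plan names no primary analysis and no accuracy measure; its only named test is a t-test with no stated comparison

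*Combined protocol and SAP*

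**What the plan says.** All references are to the combined protocol and SAP.

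- **Aim** (Justification, Objective, & Research Design, item 1): "To determine if a new assay to detect early biofilm colonization can be validated in acute postoperative wound infections".
- **Primary outcome** (Sample Size and Data Analysis, item 1): patients becoming infected during follow-up, described as "the primary outcome of the study that we are trying to ultimately be able to predict".
- **What the form asks** (same section, item 2): among other things, "which is the primary comparison/analysis, and how the analyses proposed will relate to the primary purposes of the study".
- **What the plan answers**: one sentence on descriptive statistics for age, injury, surgery and outcome, then "We will use t-testing and other statistical analysis as appropriate". The assay result is not mentioned. The t-test has no variable, groups or time point.
- **Other text linking assay and outcome**: Study Procedures, item 1, and the repeated text in Prospective Samples, item 2, say the team will "prospectively correlate the laboratory findings with clinical findings" by searching medical records to "find outcomes such as a biofilm formation". Protected Health Information, item 2, says: "Patient records will be accessed to determine clinical correlation to biofilm assay".
- **Separate protocol** (Research Protocol, item 2): the upload table reads "There are no items to display".

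**The concern.** Validating a test means estimating how often it is right in patients with the condition and in patients without it. Neither a comparison of means nor a correlation with no named statistic gives that. Followed as written, the study could enrol 1,000–1,200 patients, draw blood repeatedly, and reach analysis with no pre-planned estimate of how well the assay detects or predicts infection. The outcome definition, the draw, the cut-off and the patient group could then all be chosen after the data are seen.

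A secondary risk comes from the case mix. Patients who already have an infection at the draw are enrolled alongside patients followed for later infection (Justification, item 2; Study Procedures, item 1; Eligibility, inclusion criterion 1). The plan does not say the two groups are analysed separately. The use claimed for the assay is early warning (Lay Summary; Study Procedures, item 2). If the groups were combined, recognition of established infection could be read as early prediction.

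**Working it through.** **1. The plan's own figure.** The enrolment of 1,000–1,200 cannot be reproduced. No alpha, power, effect size, infection rate, target accuracy or precision is given. The core of the point is therefore textual.

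**2. Aim against plan.**

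| Needed for an accuracy analysis | What the documents give |
|---|---|
| Primary analysis | Asked for by the form; not given |
| Accuracy measure | None planned in any section supplied |
| Assay readout | Culture/colonization or immune response (Sample Collection/Analysis, item 4); no scale or cut-off |
| Reference standard | Comparators visible, none designated: routine cultures on readmission for suspected infection (Study Procedures, item 2); blood culture results, surgeon evaluation and a clinical diagnosis of infection (Study Procedures, item 1); a Diagnosis of Infection Form (Additional Documents), content not shown |
| Detection or prediction | Both kinds of patient enrolled; separate analysis not stated |
| Repeat draws in one patient | Draws at the initial and later visits (Study Procedures, item 1); no analysis rule |

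**3. Illustration: a significant t-test is not validation.** This applies only if the t-test were used on a continuous, normally distributed readout with equal variances, which the plan does not say. Assume one value per patient, two-sided 5%, 80% power and 10–20% infected.

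- Detectable standardized difference: d = (1.96 + 0.84) × √(1/n_inf + 1/n_non). Equivalent AUC = Φ(d/√2).
- N = 1,200, 10% infected (120 v 1,080): d = 0.27, AUC 0.58. At the midpoint cut-off, sensitivity = specificity = Φ(d/2) = 55%.
- N = 1,200, 20% infected (240 v 960): d = 0.20, AUC 0.56.
- N = 1,000, 10% and 20% infected: d = 0.30 and 0.22, AUC 0.58 and 0.56.

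So a marker that barely discriminates would usually reach significance at this sample size.

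**4. Illustration: the effect of pooling, if it happened.** Let q be the share of infections present at entry, S_d the assay's sensitivity for them, and S_p its positive rate both in uninfected patients and in those infected later (no predictive value, by assumption). Pooled sensitivity = q·S_d + (1 − q)·S_p.

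- S_d = 80%, S_p = 10%, q = 50%: 0.5 × 0.80 + 0.5 × 0.10 = 45%, at 90% specificity.
- q = 25% or 75%: 27.5% or 62.5%.
- With 10% of 1,200 infected (also assumed): 54 of 120 pooled (Wilson 95% CI 36–54%) against 6 of 60 (CI 5–20%) for later infection alone.

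Every rate here is an assumption. The example shows the direction of the error, not its likely size.

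**5. Precision of the proposed analysis.** Assume a sensitivity of 80%, 10% of 1,200 infected, and half of those infected at entry.

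- All infections: 1,200 × 0.10 = 120; Wilson 95% CI for 96/120 is 72–86%.
- Later infections only: 120 × 0.5 = 60; Wilson 95% CI for 48/60 is 68–88%.

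**The case against.** The strongest reply is that the text leaves room for a proper analysis. Its open-ended second half could include accuracy measures, and the stated intention to correlate shows that assay and outcome will be compared. That is fair as to intent. But the form asked for the primary analysis and its link to the purpose, and the wording commits to nothing.

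Some stronger readings are tempting but not supported:

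- **That no primary outcome is named.** Infection on follow-up is named. What is missing is an analysis attached to it.
- **That the study has no comparator.** Cultures, surgeon evaluation and clinical diagnosis all appear, and the unseen infection form may hold a definition. The gap is that none is designated as the reference standard. Routine culture is described only for patients readmitted with suspected infection.
- **That the plan pools infected and later-infected patients.** It does not say so. The sample-size text mentions validation and follow-up for infection as separate purposes, and infected patients may have additional draws. Only the lack of a stated separation can be criticised. The pooling example also assumes no predictive value, whereas the Lay Summary reports detection up to 1 month before clinical detection in an animal model.
- **That the t-test is the intended validation test.** Its use is unstated; it may concern patient characteristics.
- **That the readout is yes/no.** No scale is given, so both illustrations are conditional on the readout.
- **That outcome assessment is unblinded, or that participants are put at risk.** Sharing of Results already blinds treating surgeons and keeps results out of care. What remains open is the study team's own record review.

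**Conclusion.** The point holds. The study's central question, how well the assay identifies or predicts infection, has no planned primary analysis and no planned accuracy measure, and the one named test would not answer it. This rests on the text alone and needs no assumption.

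The possible mixing of detection and prediction is a secondary risk inferred from silence. Its size depends on the infection rate, the share infected at entry and the assay's accuracy, none of which the documents give. The figures for the t-test and for pooling are illustrations only. The damage would be to the study's conclusion, not to participants' care.

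**What to change.** In Sample Size and Data Analysis, item 2, replace the t-test sentence with:

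> The primary analysis estimates the sensitivity and specificity of the assay, with 95% CIs (and the AUC if the readout is continuous), against a designated reference standard for infection assigned without knowledge of the assay result. Infection already present at the draw (detection) and infection diagnosed after the draw (prediction) are analysed separately, and which is primary is stated in advance. Intervals account for repeat draws within a patient. T-tests are descriptive only.

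Because surgeons are already blinded, the blinding clause matters only for the study team's record review. The investigators must choose the reference standard and the primary target. Prediction follows from the named primary outcome, but the stated aim can also be read as detection.

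**Cost.** No new patients or samples, and a little more analysis work. Intervals for prediction are wider than for all infections together, as in step 5 of the working.

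**Optional, not part of the required change:** a rule for the index draw, a rule for incomplete follow-up, and a correction if the cut-off is chosen from the study data.

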## Sharing of Results

1 \* Describe whether results (study results or individual subject results, such as results of investigational diagnostic tests, genetic tests, or incidental findings) will be shared with subjects or others (e.g., the subject's primary care physicians) and if so, describe how it will be shared:

Results will not be shared with anyone but the study team. This data will be blinded from any treating surgeons and will not be used to affect patient care.

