## Resources

If this study is a collaborative UM/VA study, please clarify which resources are being used at each institution.

- 1 **\* Describe the time that the Principal Investigator will devote to conducting and completing the research:**  
PI will be involved in consenting and ongoing monitoring of data. Most of the sample collection and analysis will be conducted by other trained staff members and in the laboratory of Sub-Investigator ([name]).
- 2 **\* Describe the facilities where research procedures are conducted:**  
Shock Trauma Outpatient Clinic  
Lab of [name] (University of Maryland Dental School)
- 3 **\* Describe the availability of medical and/or psychological resources that subjects might need as a result of anticipated consequences of the human research:**  
Available through the outpatient clinic staff members. Patients will be referred to outside providers if needed.
- 4 **\* Describe the process to ensure that all persons assisting with the research are adequately informed about the protocol, the research procedures, and their duties and functions:**  
Patients will be given informed consent by a member of the research staff. They will then be allowed to ask any questions to the staff regarding the project prior to signing the consent document. They will be given a copy of the consent form as well.

ID: VIEW4DF83CB976400  
Name: v2\_Resources

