## Recruitment

1 \* Describe plans for recruitment, including the identification of potential participants (or acquisition of charts/records/samples) and initial interactions with them: (If this study involves the VA please list all sites at which recruitment will take place.):  
All orthopaedic patients over age 18 attending a follow-up visit with an attending orthopaedic traumatologist will be eligible. Patients over the age of 18 admitted directly from the orthopaedic trauma clinic will be eligible. Current patients over the age of 18 that have been diagnosed with an infection. Once eligibility is confirmed the research coordinator and/or the attending surgeon will initiate the research consent conversation.

2 \* Describe measures that will be implemented to avoid participant coercion or undue influence (if not applicable to the study, enter "N/A").:  
All patients will be assured that their care is standard and will not be affected by their choice to participate. In addition, the outcome of the study will not be revealed to the patient nor their doctor, therefore participation in the study is completely voluntary.

3 \* Who will recruit participants (or acquire charts/records/samples) for this study? (Check all that apply)

PI  
 Study Staff  
 Third Party

3.1 If you are using a third party, specify Third Party Recruiters:

4 Upload any recruitment tools such as screening/telephone scripts and introductory letters (do not upload advertisements here):

Name	Created	Modified Date
There are no items to display		

ID: VIEW4E0BCAA0A6C00  
Name: v2\_Recruitment

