## Confidentiality of Data

1 \* Will stored research data contain identifiers or be able to be linked to and identify individual participants (either directly or through a code/research ID)?

Yes

No, the data will be stored de-identified/anonymous (stripped of all identifiers, no way to identify individual participants)

2 \* Where will research data be kept (address electronic and paper data as applicable)? (If this is a VA study please list specific sites that data will be kept.)

All study forms, reports, and other records that are part of the study data collection materials will be identified by coded number to maintain patient confidentiality. All paper records will be kept in locked file cabinets. All electronic records of study data will be identified by coded number. Consent procedures and forms, and the communication, transmission and storage of patient data will comply with individual site IRB requirements for compliance with The Health Insurance Portability and Accountability Act (HIPAA).

3 \* How will such data be secured?

All data will be password protected and locked in an office to which there is limited access.

4 \* Who will have access to research data?

Approved research staff and PI

5 \* Will study data or test results be recorded in the participant's medical records?

Yes  No

6 \* Will any data be destroyed? (**Please note that data for FDA regulated research and VA research cannot be deleted**)  
 Yes  No

6.1 If Yes, what data (e.g., all data, some recordings, interview notes), when and how?

7 Do you plan to obtain a Certificate of Confidentiality?  
 Yes  No

7.1 If Yes, upload your Certificate of Confidentiality. If you have not yet obtained the Certificate, please note that once it is obtained, you will need to submit an amendment to attach the document, make any needed changes to the submission and make needed changes to the Informed Consent Document.

Name	Created	Modified Date
------	---------	---------------

There are no items to display

8 \* Discuss any other potential confidentiality issues related to this study:  
N/A

ID: VIEW4E1B5265E0400  
Name: v2\_Confidentiality of Data

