## Monitoring Plan - Individual

You indicated that the monitoring will be done by an individual.

1 \* Identify the individual who will be performing the safety monitoring:  
[name]

2 \* Describe this individual's role in relation to the protocol:  
Principal investigator

3 \* What data will be reviewed?  
 Adverse Events  
 Enrollment Numbers  
 Patient Charts/Clinical Summaries  
 Laboratory Tests  
 Medical Compliance  
 Procedure Reports  
 Raw Data  
 Outcomes (Primary, Secondary)  
 Preliminary Analyses  
 Other

3.1 If Other, specify:

4 \* What will be the frequency of the review?

- Annually
- Bi-Annually
- Other

4.1 If Other, specify:

On an as-needed basis.

5 \* Safety monitoring results will be reported to:

- IRB
- GCRC
- Sponsor
- Other

5.1 If Other, specify:

ID: VIEW4E1B026A2A400  
Name: v2\_Monitoring Plan - Individual

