## Informed Consent Process

**If the study does not involve interaction with participants or a waiver of consent is being requested , answer "N/A" to the questions below.**

1 \* Indicate the type(s) of consent that will be involved in this study: (check all that apply)

- Not applicable (study may qualify as exempt)
- Request to Waive Consent/Parental Permission (Consent is not being obtained)
- Request to Alter Consent (Some Elements of Consent Waived)
- Request to Waive Documentation of Consent (Verbal/Oral Consent)
- Written Consent Form**
- Electronic Consent

2 \* Describe the Informed Consent process in detail:

To encourage a high level of participation from eligible patients, the attending surgeon will be involved in the consent conversation. The conversation will be initiated by the research coordinator and/or the surgeon together. Patients will be informed of the study and intended use of blood samples obtained and any relevant data that will be collected or analyzed in conjunction with the study. Patients and their families will be provided with copies of the consent form describing the study, the risks and benefits of participation and what will be expected of them if they choose to participate.

Any participant who is enrolled in the study via consent of a Legally Authorized Representative will be re-evaluated during follow-up and will then sign the consent form if they are determined competent.

3 Confirm that the consent process will explain the following:

- The activities involve research.
- The procedures to be performed.
- That participation is voluntary.
- The name and contact information for the investigator.

\*  Yes  No

4 \* Describe who will obtain Informed Consent:

The conversation will be initiated by the research coordinator and/or the treating surgeon.

5 \* If obtaining consent from a legally authorized representative (LAR), describe how you will confirm that the individual is the LAR and can provide legally effective informed consent. (Answer "N/A" if not obtaining consent from LARs)  
LAR will be confirmed by providing ID. These will be used in the case of minors, however we are not specifically targeting this group for enrollment.

6 \* Describe the setting for consent:

All interaction will occur in private patient areas where curtains can be drawn or doors closed in the orthopaedic trauma clinic.

7 \* Describe the provisions for assessing participant understanding:

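### The blind covers treating surgeons only; nothing keeps those who record infection status from knowing the assay result

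*Combined protocol and SAP*

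**What the plan says.** Two places state a blind. Sharing of Results, item 1, reads "Results will not be shared with anyone but the study team. This data will be blinded from any treating surgeons" and adds that the data "will not be used to affect patient care". Recruitment, item 2, says that "the outcome of the study will not be revealed to the patient nor their doctor".

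Other sections describe who handles the data:

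- Confidentiality of Data, item 4, gives access to "Approved research staff and PI" and draws no line between assay data and outcome data.
- Resources, item 1: "PI will be involved in consenting and ongoing monitoring of data". Monitoring Plan - Individual, item 2, gives the safety monitor's role as "Principal investigator".
- Study Procedures, item 1: the research coordinator interviews patients at each follow-up visit, and "we would prospectively correlate the laboratory findings with clinical findings by searching the patients' medical records to find outcomes". Protected Health Information, item 2, likewise gives correlation with the assay as the reason for opening patient records.
- Privacy of Participants, item 1: the log that matches codes to patients is available to local clinic staff.
- Informed Consent Process, item 4: "The conversation will be initiated by the research coordinator and/or the treating surgeon".

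Sample Size and Data Analysis, item 1, names infection during follow-up as the primary outcome. The text provided gives no case definition, no adjudication and no time at which assay and outcome data are linked.

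**The concern.** The study aims to validate an assay, so infection status has to be settled without reference to the assay result. The stated blind protects the bedside. It does not reach the step at which somebody reads the chart and records whether, and when, the patient became infected.

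If that person knows the assay result, doubtful cases will tend to be resolved in its direction. The assay then contributes to its own reference standard, and agreement between the two is partly manufactured. Analysis cannot undo this once results have been seen, and the primary outcome is the variable affected.

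**Working it through.** The plan offers no figure to reproduce. Enrolment of 1000-1200 is stated without an infection rate, accuracy target, alpha or power. The check is a reading of the text, followed by an illustration.

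**Reading the text**

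1. Who may see assay results? The study team (Sharing of Results); for research data generally, approved staff and the principal investigator (Confidentiality of Data).
2. Who is excluded? Treating surgeons, and the patient and the patient's doctor (Recruitment). The coordinator, the abstractor and the principal investigator are not excluded.
3. Who finds the outcome? The team, in an activity described together with the correlation. No order, lock or blinded abstractor is stated.
4. Does sample coding close the gap? No. Under Prospective Samples, item 4, the code hides obvious identifiers. Clinic staff hold the key, so anyone on the clinic side with both key and results can link them.
5. Who is unaffected? Patients enrolled with a known infection, who are eligible under inclusion criterion 1. Their status was set before any study assay.

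**Illustration A (all inputs assumed)**

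Take 1200 patients: 100 clear infections, 100 equivocal cases and 1000 clear non-infections. The assay is useless and positive in 30% of each group. The Youden index is sensitivity + specificity - 1.

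- Equivocal cases called without the assay: sensitivity 0.30, specificity 0.70, Youden 0.
- All equivocal cases called in line with the assay: 30 become infected and 70 non-infected. Sensitivity = (30 + 30)/(100 + 30) = 60/130 = 0.462. Specificity = (700 + 70)/(1000 + 70) = 770/1070 = 0.720. Youden = 0.462 + 0.720 - 1 = 0.18.
- Half called in line with the assay, the other half called infected at 30% regardless of it: infected equivocal cases are 15 + 0.3 × 15 = 19.5 assay-positive and 0.3 × 35 = 10.5 assay-negative. Sensitivity = 49.5/130 = 0.381. Specificity = (700 + 59.5)/1070 = 0.710. Youden = 0.09.

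Within this scenario 0.18 is the ceiling, because every equivocal case follows the assay.

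**Illustration B (all inputs assumed except N = 1200)**

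Again the assay is useless. Let p be the true infection rate, q the assay positivity, and e the fraction of uninfected assay-positive patients recorded as infected because the result is known.

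TP = N[pq + (1-p)qe]; FN = Np(1-q); FP = N(1-p)q(1-e); TN = N(1-p)(1-q).

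The apparent odds ratio TP × TN/(FN × FP) reduces to [p + (1-p)e]/[p(1-e)], which does not depend on N or q. For p = 0.10 and e = 0.10 it is (0.10 + 0.09)/0.09 = 2.11. The true value is 1.

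| p | e = 0.05 | e = 0.10 | e = 0.20 |
|---|---|---|---|
| 0.05 | 2.05 | 3.22 | 6.00 |
| 0.10 | 1.53 | 2.11 | 3.50 |
| 0.20 | 1.26 | 1.56 | 2.25 |

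At p = 0.10 and q = 0.30, apparent sensitivity rises from 0.30 to between 0.38 (e = 0.05) and 0.55 (e = 0.20). With q from 0.10 to 0.30, the apparent Youden index runs from 0.118 + 0.905 - 1 = 0.02 (p = 0.20, q = 0.10, e = 0.05) to 0.673 + 0.745 - 1 = 0.42 (p = 0.05, q = 0.30, e = 0.20).

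Both illustrations show what knowledge of the result could do. Neither shows that it will happen. Both also presume a positive/negative cut-off, which the plan does not set.

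**The case against.** The strongest reply is that the blind is stated twice, use of results in care is barred, and the assay is run on coded samples in a separate laboratory at the dental school. If results stay there until outcomes are fixed, the blind holds. That is correct. A reader might infer that the blind cannot hold because the team includes surgeons who treat the patients. The documents do not support this. They do not say that the principal investigator, or anyone else with data access, is a treating surgeon; the team details were not available for this review; and joining a consent conversation does not confer access to assay data.

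Other parts of the reply also stand. The entries showing which data the principal investigator reviews as monitor are not legible, and ongoing monitoring is not said to include assay values. No section says that the coordinator sees results or classifies infection. Cultures are routine on readmission for suspected infection (Study Procedures, item 2), which adds a more objective element. A Diagnosis of Infection Form is listed under Additional Documents; its content was not available, and it may say who classifies infection.

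A reader might also infer that earlier dating of infection would inflate the assay's lead time. It would do the reverse: lead time runs from assay positivity to clinical diagnosis, so an earlier diagnosis date shortens it.

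None of this supplies the missing rule. The blind as written does not extend to those who record the outcome, and a laboratory hold that would protect it is nowhere stated.

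**Conclusion.** The concern holds as a gap in the plan. Treating surgeons are blinded on paper, but the chart abstractor, coordinator and principal investigator are not, and the plan does not say when assay and outcome are linked. For patients not already infected at enrolment, independence of infection status from the assay is not assured, and apparent accuracy could be inflated.

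The size cannot be determined from the documents. Under Illustration A a useless assay reaches a Youden index of at most 0.18; under Illustration B the range is 0.02 to 0.42. These figures rest on assumed infection rates, assay positivity and degree of influence. The share of patients already infected at enrolment is not given. No conclusion is drawn about surgeons' access to results, bias in bedside diagnosis or inflated lead time.

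**What to change.** In Sharing of Results, item 1, replace the release to the study team with wording such as: *Assay results are held by the laboratory under code. They are not released to the principal investigator, the research coordinator, any attending surgeon or any chart abstractor until infection status has been recorded and locked for all patients: with its date if infected, or as infection-free at last follow-up if not.* The second branch is needed because uninfected patients have no infection date, and Study Procedures, item 3, sets no fixed end of follow-up.

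In Confidentiality of Data, item 4, and Monitoring Plan - Individual, limit research-staff access and the principal investigator's monitoring to data without assay values until that lock.

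The cost is wording in three sections and an access restriction on the laboratory file, with no extra staff or visits. Care is unaffected, since the plan already bars use of the results in care. The downside is that the principal investigator cannot look at assay results against outcomes while the study runs.
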